2. DEFINITIONS

Potential Hy's Law (PHL)

AST or ALT $\geq 3 \times$ ULN **together with** TBL $\geq 2 \times$ ULN at any point during the study following the start of study medication irrespective of an increase in ALP.

Hy's Law (HL)

AST or ALT $\geq 3 \times$ ULN **together with** TBL $\geq 2 \times$ ULN, where no other reason, other than the IP, can be found to explain the combination of increases, e.g., elevated ALP indicating cholestasis, viral hepatitis, another drug.

For PHL and HL the elevation in transaminases must precede or be coincident with (i.e., on the same day) the elevation in TBL, but there is no specified timeframe within which the elevations in transaminases and TBL must occur.

3. IDENTIFICATION OF POTENTIAL HY'S LAW CASES

In order to identify cases of PHL it is important to perform a comprehensive review of laboratory data for any subject who meets any of the following identification criteria in isolation or in combination:

- ALT $\geq 3 \times$ ULN
- AST $\geq 3 \times$ ULN
- TBL $\geq 2 \times$ ULN

Central laboratories being used:

When a subject meets any of the PHL identification criteria, in isolation or in combination, the central laboratory will immediately send an alert to the Investigator (also sent to AstraZeneca representative).

The Investigator will also remain vigilant for any local laboratory reports where the identification criteria are met, where this is the case the Investigator will:

- Request a repeat of the test (new blood draw) by the central laboratory without delay
- Complete the appropriate unscheduled laboratory CRF module(s) with the original local laboratory test result

When the identification criteria are met from central or local laboratory results, the Investigator will without delay:

- Determine whether the patient meets PHL criteria (see Section 2 of this Appendix for definition) by reviewing laboratory reports from all previous visits (including both central and local laboratory results)

Local laboratories being used:

The Investigator will without delay review each new laboratory report and if the identification criteria are met will:

- Determine whether the patient meets PHL criteria (see Section 2 Definitions within this Appendix for definition) by reviewing laboratory reports from all previous visits
- Promptly enter the laboratory data into the laboratory CRF

4. FOLLOW-UP

4.1 Potential Hy's Law Criteria not met

If the patient does not meet PHL criteria the Investigator will:

- Perform follow-up on subsequent laboratory results according to the guidance provided in the CSP.

4.2 Potential Hy's Law Criteria met

If the patient does meet PHL criteria the Investigator will:

- Determine whether PHL criteria were met at any study visit prior to starting study treatment (see Section 6 of this Appendix)
- Notify the AstraZeneca representative who will then inform the central Study Team
- Within 1 day of PHL criteria being met, the Investigator will report the case as an SAE of PHL; serious criteria 'important medical event' and causality assessment 'yes/related' according to CSP process for SAE reporting
- For subjects that met PHL criteria prior to starting IP, the Investigator is not required to submit a PHL SAE unless there is a significant change[#] in the patient's condition
- The Study Physician contacts the Investigator, to provide guidance, discuss and agree an approach for the study patients' follow-up and the continuous review of data.
 - Subsequent to this contact the Investigator will:
 - Monitor the patient until liver biochemistry parameters and appropriate clinical symptoms and signs return to normal or baseline levels, or as long as medically indicated. Complete the follow-up SAE Form as required
 - Investigate the aetiology of the event and perform diagnostic investigations as discussed with the Study Physician. This includes deciding which the tests available in the HL lab kit should be used
 - Complete the 3 Liver CRF Modules as information becomes available

5. REVIEW AND ASSESSMENT OF POTENTIAL HY'S LAW CASES

The instructions in this Section should be followed for all cases where PHL criteria are met.

As soon as possible after the biochemistry abnormality was initially detected, the Study Physician contacts the Investigator in order to review available data and agree on whether there is an alternative explanation for meeting PHL criteria other than DILI caused by the IP, to ensure timely analysis and reporting to health authorities within 15 calendar days from date PHL criteria was met. The AstraZeneca Global Clinical Lead or equivalent and Global Safety Physician will also be involved in this review with other subject matter experts as appropriate.

According to the outcome of the review and assessment, the Investigator will follow the instructions below.

Where there is an agreed alternative explanation for the ALT or AST and TBL elevations, a determination of whether the alternative explanation is an AE will be made and subsequently whether the AE meets the criteria for an SAE:

- If the alternative explanation is **not** an AE, record the alternative explanation on the appropriate CRF
- If the alternative explanation is an AE/SAE: update the previously submitted PHL AE/SAE CRFs accordingly with the new information (reassessing event term; causality and seriousness criteria) following the AstraZeneca standard processes

If it is agreed that there is **no** explanation that would explain the ALT or AST and TBL elevations other than the IP:

- Send updated SAE (report term 'Hy's Law') according to AstraZeneca standard processes.
 - The 'medically important' serious criterion should be used if no other serious criteria apply
 - As there is no alternative explanation for the HL case, a causality assessment of 'related' should be assigned

If, there is an unavoidable delay, of over 15 calendar days in obtaining the information necessary to assess whether or not the case meets the criteria for HL, then it is assumed that there is no alternative explanation until such time as an informed decision can be made:

- Provides any further update to the previously submitted SAE of PHL, (report term now 'Hy's Law case') ensuring causality assessment is related to IP and seriousness criteria is medically important, according to CSP process for SAE reporting

- Continue follow-up and review according to agreed plan. Once the necessary supplementary information is obtained, repeat the review and assessment to determine whether HL criteria are still met. Update the previously submitted PHL SAE report following CSP process for SAE reporting, according to the outcome of the review and amending the reported term if an alternative explanation for the liver biochemistry elevations is determined

6. ACTIONS REQUIRED WHEN POTENTIAL HY'S LAW CRITERIA ARE MET BEFORE AND AFTER STARTING STUDY TREATMENT

This Section is applicable to patients with liver metastases who meet PHL criteria on study treatment having previously met PHL criteria at a study visit prior to starting study treatment.

At the first on-study treatment occurrence of PHL criteria being met the Investigator will determine if there has been a significant change in the patients' condition[#] compared with the last visit where PHL criteria were met[#]

- If there is no significant change, no action is required
- If there is a significant change, notify the AstraZeneca representative, who will inform the central Study Team, then follow the subsequent process described in Section 4.2 of this Appendix

[#] A 'significant' change in the patient's condition refers to a clinically relevant change in any of the individual liver biochemistry parameters (ALT, AST or TBL) in isolation or in combination, or a clinically relevant change in associated symptoms. The determination of whether there has been a significant change will be at the discretion of the Investigator, this may be in consultation with the Study Physician if there is any uncertainty.

7. ACTIONS REQUIRED FOR REPEAT EPISODES OF POTENTIAL HY'S LAW

This Section is applicable when a patient meets PHL criteria on study treatment and has already met PHL criteria at a previous on study treatment visit.

The requirement to conduct follow-up, review and assessment of a repeat occurrence(s) of PHL is based on the nature of the alternative cause identified for the previous occurrence.

The Investigator should determine the cause for the previous occurrence of PHL criteria being met and answer the following question:

Was the alternative cause for the previous occurrence of PHL criteria being met found to be the disease under study, e.g., chronic or progressing malignant disease, severe infection or liver disease, or did the patient meet PHL criteria prior to starting study

treatment and at their first on study treatment visit (as described in Section 6 of this Appendix)?

If No: Follow the process described in Section 4.2 of this Appendix for reporting PHL as an SAE.

If Yes: Determine if there has been a significant change in the subject's condition[#] compared with when PHL criteria were previously met.

- If there is no significant change no action is required
- If there is a significant change follow the process described in Section 4.2 of this Appendix for reporting PHL as an SAE

[#] A 'significant' change in the patient's condition refers to a clinically relevant change in any of the individual liver biochemistry parameters (ALT, AST or TBL) in isolation or in combination, or a clinically relevant change in associated symptoms. The determination of whether there has been a significant change will be at the discretion of the Investigator; this may be in consultation with the Study Physician if there is any uncertainty.

8. LABORATORY TESTS

The list below represents the standard, comprehensive list of follow-up tests which are recommended but not mandatory when using a central laboratory. For studies using a local laboratory, the list may be modified based on clinical judgement. If required, additional assistance on which tests could be used to evaluate other potential causes of liver dysfunction consult with the Hepatic Safety Knowledge Group. Any test results need to be recorded.

Law lab kit for central laboratories (18 December 2018)

Additional standard chemistry and coagulation tests	GGT LDH Prothrombin time INR
Viral hepatitis	IgM anti-HAV IgM and IgG anti-HBc HBsAg HBV DNA IgG anti-HCV HCV RNA* IgM anti-HEV HEV RNA
Other viral infections	IgM & IgG anti-CMV IgM & IgG anti-HSV IgM & IgG anti-EBV
Alcoholic hepatitis	CD-transferrin**

Autoimmune hepatitis	ANA Anti-LKM Ab ASMA
Metabolic diseases	Alpha-1-antitrypsin Ceruloplasmin Iron Ferritin Transferrin Transferrin saturation

* HCV RNA is only tested when IgG anti-HCV is positive or inconclusive

** CD-transferrin is not available in China. Study teams should amend this list accordingly

Abbreviations: Ab=antibody; ANA=antinuclear antibody; ASMA=anti-smooth muscle Ab; CD=carbohydrate deficient; CMV=cytomegalovirus; DNA=deoxyribonucleic acid; EBV=Epstein-Barr virus; GGT=gamma-glutamyl transferase; HAV=Hepatitis A virus; HBc=Hepatitis B core; HBsAg=Hepatitis B surface antigen; HBV=Hepatitis B virus; HCV=Hepatitis C virus; HEV= Hepatitis E virus; HSV=Herpse simplex virus; IgG=Immunoglobulin G; IgM=Immunoglobulin M; INR=international normalized ratio; LDH=lactate dehydrogenase; LKM=liver/kidney microsomal; RNA=ribonucleic acid.

REFERENCES

FDA Liver Guidance Document 2009 Guidance for Industry: Drug Induced Liver Injury – Premarketing Clinical Evaluation.

Revision History

Version	Description of Change
1.0	The previous version of the Hy's Law Appendix E was not numbered. Version numbering introduced with version 2.0 of the SOP Detection and Handling of Potential Hy's Law Cases And Hy's Law Cases In Clinical Studies AZDoc0007120 Document revised with updated SOP.
2.0	Section 8 Laboratory Tests revised to clarify tests are recommended. Table of tests updated to include footnotes.

Appendix H MEDI4736 Adverse Events of Special Interest

1. MEDI4736 ADVERSE EVENTS OF SPECIAL INTEREST

1.1 Immune-related adverse events (general)

An immune-related AE (irAE) is defined as a clinically significant AE of unknown etiology of any organ that is associated with drug exposure and is consistent with an immune-mediated mechanism. Serologic, immunologic, and histologic (biopsy) data should be used to support an irAE diagnosis. Appropriate efforts should be made to rule out neoplastic, infectious, metabolic, toxin, or other etiologic causes of the irAE.

If the Investigator has any questions in regards to an AE being an irAE, the Investigator should immediately contact the Study Physician.

1.2 Pneumonitis

If new or worsening pulmonary symptoms (e.g., dyspnoea or cough) or radiological abnormalities occur in the absence of a clear diagnosis, an interruption in study treatment dosing is recommended and further diagnostic work-up should be performed to exclude pneumonitis. The differential diagnosis should include the possibility of both immune-related and non-immune related processes. AEs of pneumonitis are of interest for AstraZeneca as pneumonitis has been observed with use of anti-PD-1 monoclonal antibodies (mAbs), (although not with anti-PD-L1 mAbs), and instances of pneumonitis have been reported in patients undergoing olaparib treatment.

Initial work-up should consider the inclusion of a clinical evaluation, high-resolution CT scan, ruling out infection, pulse oximetry, and other appropriate laboratory work-up. Pulmonary consultation is highly recommended. Guidelines for the management of patients with irAEs including pneumonitis are provided in MEDI4736 Annex 1.

Following investigation, if no evidence of abnormality is observed on CT imaging and symptoms resolve, then study treatment can be restarted, if deemed appropriate by the Investigator. If significant pulmonary abnormalities are identified, these need to be discussed with the Study Physician.

1.3 Infusion reactions

AEs of infusion reactions (also termed infusion-related reactions) are of special interest to AstraZeneca and are defined, for the purpose of this CSP, as all AEs occurring from the start of study drug infusion up to 48 hours after the infusion start time. For all infusion reactions, the eCRF should be completed as instructed in Section 7.1.4, and all SAEs should be reported to AstraZeneca Patient safety as described in Section 7.1.5.

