6.3 Definitions of adverse events of special interest

AEs of special interest (AESIs) are events of scientific and medical interest for the further understanding of the AZD9150, AZD5069, tremelimumab, and MEDI4736 safety profiles and require close monitoring and rapid communication by the Investigator to AstraZeneca. Such AESIs may be serious or non-serious. The rapid reporting of these AESIs allows ongoing analysis of these events in order to characterise and understand them in association with the use of these IPs.

MEDI4736, an anti-PD-L1 antibody, binds with high affinity and specificity to PD-L1 and blocks its binding to PD-1 (CD279) and B7-1 (CD80) molecules, thus promoting anti-tumor immunity and tumor cell killing. Potential risks based on these mechanisms of action include immune-mediated reactions such as enterocolitis, dermatitis, hepatotoxicity or hepatitis, endocrinopathy, neuropathy or neurologic events, pancreatitis, and pneumonitis. More specific guidelines for their evaluation, reporting, and treatment are described in detail for MEDI4736 in Annex 1. Further information on these risks (e.g., presenting symptoms) can also be found in the current edition of the MEDI4736 (durvalumab) IB.

AZD5069, an inhibitor of CXCR2, acts by modulating neutrophil migration and has been shown to weakly bind the hERG receptor. Therefore, effects on neutrophil count, including reduction in their number (neutropenia), infections (especially requiring the administration of outpatient oral or IV antibiotics) are deemed of special interest, as are ECG abnormalities arising after the beginning of treatment with this agent.

At present, there are no AESIs for AZD9150.

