6.9.2 Infusion reactions

In order to help understand the potential drug relatedness of any acute reaction, a blood sample should be drawn during the event for possible additional ADA testing. Serum tryptase or other blood or urine testing relevant to the diagnosis of anaphylaxis may be obtained at the discretion of the Investigator.

In the event of a grade 2 infusion related reaction as determined by the Investigator, the infusion should be interrupted and restarted at the same rate as the original infusion after symptomatic treatment (e.g., antihistamines, nonsteroidal anti-inflammatory drugs, narcotics, and IV fluids) and resolution of the reaction.

In the event of a grade 3 infusion related reaction, the infusion should be interrupted and restarted at half the rate after symptomatic treatment and resolution of the reaction. If the infusion reaction returns to grade 3 or greater, the patient should discontinue the study treatment permanently.

In the event of a grade 4 infusion-related reaction, the patient should discontinue the study treatment permanently.

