An immune-mediated AE (imAE) is defined as an AESI that is associated with drug exposure and is consistent with an immune-mediated mechanism of action and where there is no clear alternate aetiology. Serologic, immunologic, and histologic (biopsy) data, as appropriate, should be used to support an imAE diagnosis. Appropriate efforts should be made to rule out neoplastic, infectious, metabolic, toxin, or other etiologic causes of the imAE.

If the Investigator has any questions in regards to an event being an imAE, the Investigator should promptly contact the Study Physician.

AESIs observed with durvalumab ± tremelimumab include:

- Diarrhoea / Colitis and intestinal perforation
- Pneumonitis / ILD
- ALT/AST increases / hepatitis / transaminase increases / hepatotoxicity
- Neuropathy / neuromuscular toxicity (e.g., Guillain-Barré and myasthenia gravis)
- Endocrinopathies (i.e., events of hypophysitis/ hypopituitarism, adrenal insufficiency, diabetes insipidus, hyperthyroidism, hypothyroidism, and type I diabetes mellitus)
- Rash / Dermatitis
- Nephritis / Blood creatinine increases
- Pancreatitis / serum (or labs suggestive of pancreatitis - increased serum lipase and , increased serum amylase increases)

- Myocarditis
- Myositis / Polymyositis
- Neuropathy / neuromuscular toxicity (e.g., Guillain-Barré, and myasthenia gravis)
- Other inflammatory responses that are rare/less frequent with a potential immune-mediated aetiology include, but are not limited to, myocarditis, pericarditis, sarcoidosis, and uveitis and other events involving the eye, skin, haematological and rheumatological events.

In addition, infusion-related reactions and hypersensitivity/anaphylactic reactions with a different underlying pharmacological aetiology are also considered AESIs.

Further information on these risks (e.g., presenting symptoms) can be found in the current edition(s) of the durvalumab and tremelimumab IBs. More specific guidelines for their evaluation and treatment are described in detail in the Dosing Modification and Toxicity Management Guidelines (see Annex 1). These guidelines have been prepared by the Sponsor to assist the Investigator in the exercise of his/her clinical judgement in treating these types of toxicities. These guidelines apply to AEs considered causally related to the study drug/study regimen by the reporting Investigator.

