If the actual weight is less than the IBW or the patient is less than 5 feet tall, the actual weight will be used to determine dose.

Weight obtained on Day -7 of the lead-in will be used to calculate the weight-related doses of AZD9150 for the lead-in. Weight obtained on Day 1 of each cycle will be used to calculate the weight-related dose of AZD9150 for each cycle.

During the 7-day lead-in period, AZD9150 will be administered as a loading dose on Days -7, -5, and -3. A window of +1 day per loading dose is allowed. Doses should not be given on back-to-back days. Starting with Cycle 1, AZD9150 will be administered QW on Days 1, 8, 15, and 22 of each treatment cycle; doses have a ± 2 day dosing window.

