Exposure to IP (i.e., total amount of study drug received) will be listed for all patients by cohort.

Total exposure (date of last dose minus date of first dose + 1) and total time on study (date of discontinuation minus date of first dose + 1) will be summarised by the following: Mean, standard deviation, minimum, maximum, median, and number of observations. In addition, the number and percentage of patients with at least 1 dose interruption/dose delay and at least 1 dose-reduction will be presented separately for the initial period of evaluability defined as 28 days and for any time following this initial period of the study.

Relative dose intensity and percentage intended dose for AZD9150, AZD5069, and MEDI4736 will be derived and summarised by the following: Median, minimum, maximum, 75th percentile, 25th percentile, and number of observations. Relative dose intensity is the percentage of actual dose intensity delivered relative to the intended dose intensity through treatment discontinuation. The entire intended treatment period will be used in the derivation of relative dose intensity.

Safety

No inferential testing will be performed on safety data. Safety data will be summarised using descriptive statistics. At the end of the study, appropriate summaries of all safety data will be produced, as defined below.

AEs will be listed individually by patient and treatment group. For patients who have a dose modification, all AEs (due to drug or otherwise) will be assigned to the associated initial dose combination/treatment dose.

AESIs will also be summarised and listed separately for each compound.

The number of patients experiencing each AE will be summarised by the Medical Dictionary for Regulatory Activities (MedDRA) system organ class, MedDRA preferred term and CTCAE grade. The number and percentage of patients with AEs in different categories (e.g., causally related, CTCAE ≥ 3) will be summarised by dose group, and events in each category will be further summarised by MedDRA system organ class and preferred term, by cohort (as appropriate). SAEs and other significant AEs will be summarised separately if a sufficient number occur.

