## Statistical Analysis Plan

### 6.2. KEY DEFINITIONS

For the purposes of this study, the term “study drug” is restricted to AZD9056, AZD9150, MEDI4736, treme, and the 4 drug combinations, AZD9056/MEDI4736, AZD9150/MEDI4736, AZD9056/MEDI4736/treme and AZD9150/MEDI4736/treme.

Study Day is the day relative to the date of the first dose of study drug in Cycle 1. If a date falls on or after the date of the first dose in Cycle 1, then the corresponding Study Day is calculated as (Study date) – (Date of first dose in Cycle 1) + 1. If a date falls before the date of first dose in Cycle 1, the corresponding Study Day is calculated as (Study date) – (Date of first dose in Cycle 1). Day -1 is the day immediately before the date of the first dose in Cycle 1.

The last dose date is defined as the last non-missing date where a non-zero dose of study drug was recorded. For patients who are ongoing at the time of an interim analysis, the last dose date will be considered the date of the most recent study visit in the database for that patient where a non-zero dose of study drug was recorded.

Unless otherwise specified, baseline is the last non-missing observation before the start of study treatment in Cycle 1.

In treatment arm A1 (AZD9150/MEDI4736), A4 (AZD9150/MEDI4736 or AZD9150/MEDI4736/treme) in dose escalation Part A, an evaluable patient must have received all 3 loading doses of AZD9150 during the 7-day Lead-in period and at least 3 additional doses during Cycle 1 as well as the MEDI4736 and treme infusion during the DLT Evaluation period or have suffered a DLT within the first 35 days of treatment. In treatment arm A2 (AZD5069/MEDI4736) in dose escalation Part A, an evaluable patient must have received all doses during the 7-day Lead-in period (i.e., 14 doses) and at least 42 additional doses as well as the MEDI4736 infusion during the DLT Evaluation period or have suffered a DLT during or before the first 35 days of treatment.

An efficacy evaluable patient is defined as a patient with unidimensional measurable disease at baseline as per the RECIST version 1.1 criteria who received at least 1 dose of study treatment.

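### The infusion-reaction AESI in protocol Appendix H is defined by a 48-hour window alone, which conflicts with Section 6.9, leaves unclear which infusions count, and would count unrelated AEs

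*Protocol*

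**What the plan says.** Appendix H is titled "Appendix H MEDI4736 Adverse Events of Special Interest". Its Section 1.3 declares infusion reactions to be of special interest and defines them, for this protocol, "as all AEs occurring from the start of study drug infusion up to 48 hours after the infusion start time". Nothing in that section restricts the events by type, grade or cause.

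Other sections treat the same event differently:

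- Section 6.9.2 starts from a graded clinical judgement: "In the event of a grade 2 infusion related reaction as determined by the Investigator".
- Section 6.9.4 asks the Investigator to examine the symptoms before settling on a diagnosis, and leaves later reactions to the Investigator's discretion.
- Section 6.9.6 lists the reactions by mechanism: "In addition, infusion-related reactions and hypersensitivity/anaphylactic reactions with a different underlying pharmacological aetiology are also considered AESIs". It gives no time window.

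On scope, Section 6.3 states: "At present, there are no AESIs for AZD9150". Appendix H 1.3 nevertheless refers to infusion of study drug, and SAP 6.2 gives that term as "restricted to AZD9056, AZD9150, MEDI4736, treme, and the 4 drug combinations". (AZD9056 there is evidently a slip for AZD5069, which is oral and opens no infusion window.)

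On analysis, protocol Section 8.10 plans: "AESIs will also be summarised and listed separately for each compound". The AE tables listed in SAP 11.3 include none for AESIs or infusion reactions, and SAP 13 records no departure from the protocol on this point.

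**The concern.** A definition by time alone captures whatever happens to start in the two days after an infusion: constipation, back pain, a fall. Section 6.3 asks for AESIs to be closely monitored and rapidly communicated, and Section 8.10 wants them summarised by compound. If the Appendix H wording is applied, the infusion-reaction count mixes true reactions with background AEs in an unknown proportion.

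If AZD9150 infusions also open a window, that proportion depends on the infusion schedule. Arms could then differ with no true difference in reactions, B7 and B8 for example. A programmer working from the two documents could not tell which definition to use or which infusions to include.

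**Working it through.** The documents give no expected infusion-reaction rate, so there is no figure of the plan's own to reproduce. The check measures how much follow-up falls inside a 48-hour window, then how many patients background AEs alone would flag.

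**Inputs from the protocol**

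- AZD9150 lead-in: 3 infusions, on Days -7, -5 and -3.
- AZD9150 in the weekly arms (Section 7.2.1): "Starting with Cycle 1, AZD9150 will be administered QW on Days 1, 8, 15, and 22 of each treatment cycle".
- AZD9150 in Arm B8: every 2 weeks, so 2 infusions per 28-day cycle (Section 4.2.2).
- MEDI4736: 1 infusion per 28-day cycle in every arm assigned it.
- AZD5069: oral.

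**Assumptions**

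- On shared days MEDI4736 starts about 2 hours after AZD9150, which lengthens the joint window by 2 hours.
- There is no true infusion effect, and background AEs arise at a constant rate r of 1, 2 or 4 per 28 days. The documents give no rate, so this is a range.
- Arms B5 and B6 are taken before any MEDI4736 is added.

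**Reading 1: only MEDI4736 infusions count.** Each arm assigned MEDI4736 has one window per cycle: 48/672 = 7.1%. The schedule creates no difference between these arms.

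**Reading 2: all study-drug infusions count.** The AZD9150 lead-in covers 3 × 48 = 144 of 168 hours (85.7%).

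| Arms | Hours covered per cycle | Share of cycle (672 h) | Share of first 35 days (840 h) |
|---|---|---|---|
| B1, B3, B7 | 4 × 48 + 2 = 194 | 28.9% | (144 + 194)/840 = 40.2% |
| B5 | 4 × 48 = 192 | 28.6% | (144 + 192)/840 = 40.0% |
| B8 | 2 × 48 + 2 = 98 | 14.6% | (144 + 98)/840 = 28.8% |
| B2, B4 | 48 | 7.1% | 48/840 = 5.7% |
| B6 | 0 | 0% | 0% |

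Over the first 35 days, B1, B3 and B7 have 338/48, or about 7 times, the window of B2 and B4.

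**Patients flagged by background AEs alone.** With H hours covered, P(at least one) = 1 − exp(−r × H/672).

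| Case | H | r = 1 | r = 2 | r = 4 |
|---|---|---|---|---|
| Reading 1, any MEDI4736 arm, one cycle | 48 | 6.9% | 13.3% | 24.9% |
| Reading 2, B1/B3/B7, one cycle | 194 | 25.1% | 43.9% | 68.5% |
| Reading 2, B8, one cycle | 98 | 13.6% | 25.3% | 44.2% |
| Reading 2, B1/B3/B7, first 35 days | 338 | 39.5% | 63.4% | 86.6% |
| Reading 2, B8, first 35 days | 242 | 30.2% | 51.3% | 76.3% |
| Reading 2, B2/B4, first 35 days | 48 | 6.9% | 13.3% | 24.9% |

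**Share of flagged events that are true.** Let t be the assumed number of true reactions per patient in the first 35 days. The share is t/(t + r × H/672). With t from 0.02 to 0.20 and r from 1 to 4, Reading 2 gives 1% to 28% in B1, B3 and B7, and 7% to 74% in B2 and B4. The documents do not narrow this.

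**The case against.** The strongest reply is about scope. Appendix H concerns MEDI4736, and Section 6.3 says AZD9150 has no AESIs, so the infusion meant in 1.3 may be the MEDI4736 infusion. All arms assigned MEDI4736 then carry the same 7.1% window and the schedule effect disappears. This stands as a possible reading. The wording does not say so, however, and Section 4.2.2 uses study drug for the monotherapy agent to which MEDI4736 is added. Background AEs are counted under either reading.

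A second reply is that a reader might infer that true infusion reactions cannot be seen at all. The documents do not support that. Section 6.4.3 collects diagnosis, grade and causality for each AE, and SAP 11.3 tabulates AEs by preferred term, by grade and by relatedness. A diagnosed reaction appears there whatever Appendix H says.

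A third reply is that a wide capture rule can serve surveillance alongside clinical diagnosis. That is fair, provided the capture is not reported as the infusion-reaction rate. Appendix H 1.3 also sends sites to Sections 7.1.4 and 7.1.5, which this protocol does not have. That suggests carried-over text rather than a deliberate choice.

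Finally, safety analyses are descriptive and the SAP lists no AESI table, so nothing shows that the 48-hour rule would be programmed. That limits the consequence but leaves the definition unspecified.

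**Conclusion.** The point holds in limited form. Appendix H 1.3 conflicts with Sections 6.9.2, 6.9.4 and 6.9.6 and is unclear on AZD9150 infusions. Used in the Section 8.10 summary, it would count background AEs as infusion reactions.

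For MEDI4736 infusions only, that means about 7% to 25% of patients per cycle, assuming 1 to 4 evenly spread AEs per 28 days. If all study-drug infusions count, covered time per cycle runs from 0% (B6) to about 29% (B1, B3, B5, B7), so rates would also differ by schedule without any true difference.

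Two stronger conclusions are tempting and not supported. One is that the AESI rate mainly measures how often an arm is infused. That needs the broad reading, plus background and true rates that the documents do not give. The other is that an event on a shared infusion day counts for both compounds. Section 6.3 leaves AZD9150 no AESI category in which to count it.

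The primary endpoint is unaffected. The issue is worth correcting because it decides what one planned safety summary reports.

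**What to change.** - Reconcile Appendix H 1.3 with Sections 6.3, 6.9.2, 6.9.4 and 6.9.6, and state which infusions count. Correct the references to Sections 7.1.4 and 7.1.5.
- For analysis, define the AESI as an AE that the Investigator reports as an infusion-related reaction, with onset on the infusion day or within the next 2 calendar days. Timing is then a necessary condition, not the whole definition. Calendar days are needed because Section 6.4.3 lists AE onset as a date only.
- Name this definition and its table in SAP 11.3. Section 6.4.3 lists causality only as yes or no against the investigational product, so the SAP should also say how events are assigned to a compound.
- If the 48-hour all-AE capture is kept for surveillance, list it separately and do not label it infusion reactions.

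The cost is a short protocol clarification, one derivation and one table. It uses data already listed as collected, unless the sponsor wants causality by compound. The downside is that a reaction the Investigator does not recognise appears only in the general AE tables. The change concerns classification and reporting, not clinical management.
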